**[name]**  
**Medical Student, Indiana University School of Medicine**

**Version 5.0 10-21-19**

## 1.0 Background

Indiana University Hospital is a large academic health center that performs a large number (~180) of cystectomies per year. Cystectomy is a urologic procedure that involves the radical removal of the bladder, with subsequent need for urinary tract reconstruction. The reconstruction requires harvesting of portions of the small and/or large bowel, and can be in the form of an ileal conduit, orthotopic bladder replacement, or continent urinary reservoir such as an "Indiana Pouch". The postoperative course usually spans on average a 7-day inpatient hospital stay, with the majority of the issues surrounding management of postoperative pain and subsequent ileus. Currently, there is no standard of pain control in cystectomy, though adjunctive mechanisms of analgesia are often utilized to decrease opioid usage. Opioid use has long been associated with postoperative ileus, nausea and vomiting, aspiration, prolonged hospital stay, and several other side effects. Postoperative pain may also decrease patient satisfaction while increasing length of hospital stay and hospital costs. Without a standard practice for postoperative pain control in cystectomy, our study aims to compare thoracic epidural versus rectus sheath block versus surgeon infiltration of local anesthesia for cystectomy. With studies indicating improvements in perioperative outcomes for all three techniques, we believe we should compare these three methods for possible incorporation of the best technique for our enhanced recovery after surgery (ERAS) protocol for cystectomy. This will be done by collection of post-operative pain scores (VAS) at both resting and with movement. The VAS (Visual Analog Scale) pain scores will be measured at 24, 48, 72 and 96 hours under an advanced recovery perioperative care pathway.

Epidural analgesia is well studied in cystectomy patients and with studies indicating improved perioperative outcomes. Ozyuvaci et al found that when combining epidural and general analgesia, radical cystectomy patients had significantly less intraoperative bleeding and pain by visual analogue scale (VAS) at 0, 1, 2, 4, 6, 12, and 24 hours when compared to general analgesia alone. Ladjevic et al saw similar results with combined epidural and general analgesia with decreased intraoperative bleeding and postoperative pain. Epidural analgesia was also associated with decreased incidence of postoperative ileus and blood transfusion requirements in a randomized clinical trial by Mazul-Sunko et al. In a study by Toren et al,

---

 H. D. de Boer, O. Detriche, and P. Forget, "Opioid-Related Side Effects: Postoperative Ileus, Urinary Retention, Nausea and Vomiting, and Shivering. A Review of the Literature," *Best Pract Res Clin Anaesthesiol* 31, no. 4 (2017).

 J. J. Pozek, M. De Ruyter, and T. W. Khan, "Comprehensive Acute Pain Management in the Perioperative Surgical Home," *Anesthesiol Clin* 36, no. 2 (2018).

 E. Ozyuvaci et al., "General Anesthesia Versus Epidural and General Anesthesia in Radical Cystectomy," *Urol Int* 74, no. 1 (2005).

 N. Ladjevic et al., "Combined General and Epidural Anaesthesia Versus General Anaesthesia for Radical Cystectomy," *Acta Chir Iugosl* 54, no. 4 (2007).

 B. Mazul-Sunko et al., "Thoracic Epidural Analgesia for Radical Cystectomy Improves Bowel Function Even in Traditional Perioperative Care: A Retrospective Study in Eighty-Five Patients," *Acta Clin Croat* 53, no. 3 (2014).

patients receiving patient-controlled epidural analgesia had significantly less pain during activity with a noted trend toward earlier tolerance of solid foods.

Surgeon infiltration has not been studied as much in cystectomy patients specifically, but it is well-studied in a wide variety of other surgeries including large pelvic surgeries. Liposomal bupivacaine injection by surgeon infiltration is associated with decreased opioid usage including rescue IV opioids and PCA use compared to bupivacaine hydrochloride with laparotomies for gynecologic malignancy. In hepatectomy for hepatocellular carcinoma, Wu et al showed improved NRS scores as well as decreased analgesic usage and intestinal function recovery time. Sun et al saw similar decreases in pain and analgesic use in open hepatectomy, but also showed decreases in surgical stress response including hormonal response, heart rate, and mean arterial pressure in the first 48-h postoperatively. In total knee arthroplasty, local wound infiltration analgesia combined with adductor canal block decreased early incisional pain in the postoperative period, decreased operative time, and promoted earlier knee joint mobility. To our knowledge, comparison between epidural analgesia and surgeon infiltration has not been studied for cystectomy.

Exparel®, a liposomal formulation of bupivacaine (LB), has shown significant promise in providing extended analgesic coverage in the postoperative period. Due to its extended release format, LB can provide analgesia coverage for up to 72 hours postoperatively when compared to normal saline and has been suggested to reduce postoperative opioid use as well (9). It has provided effective analgesia in total knee arthroplasty and hip arthroplasty and has shown promise in open and laparoscopic colectomy. However, there are also studies showing that LB might not be superior to standard bupivacaine (SB) in terms of duration of

---

 E. Kalogera et al., "Abdominal Incision Injection of Liposomal Bupivacaine and Opioid Use after Laparotomy for Gynecologic Malignancies," *Obstet Gynecol* 128, no. 5 (2016).

 Y. F. Wu et al., "Postoperative Local Incision Analgesia for Acute Pain Treatment in Patients with Hepatocellular Carcinoma," *Rev Assoc Med Bras* (1992) 64, no. 2 (2018).

 J. X. Sun et al., "Effect of Local Wound Infiltration with Ropivacaine on Postoperative Pain Relief and Stress Response Reduction after Open Hepatectomy," *World J Gastroenterol* 23, no. 36 (2017).

## 2.0 Rational and Specific Aims

All of the pain control modalities in this study have been used as postoperative analgesia in prior studies. The specific aim of this study is to compare the difference between the pain control methods in achieving the following:

1. Decreased opioid requirements
2. Improved postoperative VAS (Visual Analog Scale) pain scores
3. Decreased opioid side effects (Nausea, sedation, ileus, respiratory depression)
4. Decreased hospital length of stay (LOS)

The primary endpoint of this study will be VAS (Visual Analog Scale) pain score at both resting and with movement. The VAS Visual Analog Scale) pain score will be measured at 24, 48, 72 and 96 hours under an advanced recovery perioperative care pathway.

The secondary endpoint includes intravenous opioid consumption, opioid side effects (nausea, sedation, ileus, respiratory depression), and LOS. Hospital length of stay (LOS) will be collected via EMR of the admission and discharge date to calculate the LOS. The IV and PO opioid doses will be quantified at 1, 24, 48, 72, and 96 hours. All the opioid consumption (both PO and IV) will be converted to PO morphine equivalent for analysis. We will also measure postoperative nausea and sedation scores at 1, 24, 48, 72, and 96 hours. Nausea will be measured on a 4-point scale: none, mild, moderate or severe. This is collected as patient reported as well as per nursing documentation. Sedation score is also reported on a 4-point scale: awake/alert, quietly awake, asleep/arousable or deep sleep. This is collected as an observation by nurse coordinator/staff. We will access patient's satisfaction at 24, 48, 72 and 96 hours. This will be measured on a 5-point scale; very unsatisfied, unsatisfied, neutral, satisfied and very satisfied. We will also measure time to first flatus, postoperative creatinine, incidence of hypotension (defined as BP decrease of more than 20%), incidence of respiratory depression, and ambulation activity.

Ambulation is defined as anytime out of bed (up in chair, to bathroom and walking in hall with PT/nurse) activity will also be recorded daily. It will be recorded as yes/no.

---

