### **4.0 Enrollment/Randomization**

All cystectomy cases scheduled by the urologists at IU Health University Hospital will be identified. Subjects will be contacted face-to-face prior to surgery by one of the research team members. They will be informed about the study and all questions will be answered. The potential subjects will be given a copy of the informed consent form and authorization form. The subjects will then be contacted face-to-face in POCU on the day of surgery and if participation is agreed, written consent will be taken. All patients will undergo a standardized enhanced recovery perioperative care pathway designed and agreed upon by the perioperative team of anesthesiologists and surgeons.

A total of 160 subjects will be randomized by a computer program into four groups (40 in each group):

1. Thoracic epidural– epidural bupivacaine 0.05%/hydromorphone 0.05mg/ml mix will be given throughout the duration of their epidural analgesia.
2. Rectus Sheath Block - 20 mL of liposomal bupivacaine diluted with 40 mL of 0.125% bupivacaine and 40 ml of injectable saline for a total of 100 mL. The 100 mL will be injected into 4 locations below the rectus abdominis muscle.
3. Surgeon infiltration with Liposomal Bupivacaine (LB) – 20 mL of liposomal bupivacaine diluted with 40 mL of 0.125% bupivacaine and 40 ml of injectable saline for a total of 100 mL. The 100 mL will be injected throughout the incision site by the surgeon at the end of surgery, prior to abdominal wall closure.
4. Surgeon infiltration with Standard Bupivacaine (SB) – 60ml of 0.5% bupivacaine will be diluted with 40ml of saline for a total of 100ml. The 100 mL will be injected throughout the incision site by the surgeon at the end of surgery.

Randomization will be performed using Research Randomizer. The primary investigator will inform the person doing the block as to what group the patients are randomized to

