#### **Study procedures:**

Thoracic epidural placement will occur in the preoperative period. Both the rectus sheath block and the surgeon infiltration will occur at the end of the case. All procedures will be done using sterile technique with masks, hats, and sterile gloves. Thoracic epidurals and rectus sheath block will be placed under the supervision of the attending anesthesiologist on the acute pain service. Surgeon infiltration will be performed by the surgeon.

Patients will be randomized to one of the four arms by the research randomizer. On the day of surgery, the Principal Investigator will inform the person doing the block as to what group the patients are randomized to.

Thoracic epidural will be performed around T9-T10 interspace since that correlates with surgical incision dermatomes. Utilizing the loss-of-resistance technique, an 18-gauge needle will be inserted in the midline between the lumbar spinous processes and advanced until loss-of-resistance is felt. A small amount of preservative-free saline will be injected to ensure the location in the epidural space. After careful aspiration, a test dose of 2-3 mL local anesthetic containing diluted epinephrine will be injected and the heart rate will be monitored in case of accidental placement in an epidural vein.

---

Rectus sheath block will be performed at 4 locations below the rectus abdominis muscle, using an ultrasound. The locations will be both left and right abdomen, above and below the umbilical region.

Surgical wound infiltration will be performed by the surgeon at the end of the case. It will be performed via a direct technique. In the direct technique, anesthetic is injected after careful aspiration in small boluses into the subfascial tissues until the wound is adequately anesthetized.

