Opioid usage at 1, 24, 48, 72, and 96 hours after the block will be recorded by a member of the research team. Pain scores at rest and on movement (knee flexion) will be measured by the investigator using Visual Analog Scale (VAS). VAS will measure pain from a scale of 0-10. Nausea will be measured using a categorical scoring system (none=0; mild=1; moderate=2; severe=3). Nausea score will be reported by the patients. Anti-emetic usage will also be recorded. Sedation scores will also be assessed by a member of the study team using a sedation scale. Hospital length of stay (LOS) will be collected via EMR of the admission and discharge date to calculate the LOS. We will also measure time to first flatus, postoperative creatinine, incidence of hypotension (defined as BP decrease of more than 20% from morning of surgery), incidence of respiratory depression (defined by nursing report or naloxone use), and ambulation activity (anytime out of bed (up in chair, to bathroom and walking in hall with PT/nurse) will also be recorded daily. It will be recorded as yes/no.

All these parameters will be measured at 1, 24, 48, 72, and 96 hours after the cystectomy.

All patients will complete a phone survey approximately 6 months after surgery to assess for pain and how it impacts their daily function. This is meant to assess for the incidence of chronic post-op pain after cystectomy with all the different pain interventions. The survey will measure how their pain interfere with their general activity, mood, walking ability, normal work, relations with other people, sleep and enjoyment of life. If after four attempts to contact the patient are unsuccessful, the survey will not be completed; this will not be considered a deviation as the survey is not critical to the overall data collection.

Data management will include quality assurance and quality control measures. All collected data will be monitored by a data and safety monitoring group independent from the research team. Data quality, subject recruitment, accrual,-retention, outcome and adverse event data, assessment of scientific reports or therapeutic development, results of related studies that may impact subject safety and procedures designed to protect the privacy of subjects will be monitored at least annually.

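### The opioid outcome counts IV and oral doses only, so it measures supplemental opioid; read as total opioid requirement it favours the epidural arm, the only arm assigned epidural hydromorphone

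*Combined protocol and SAP*

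**What the plan says.** Section 2.0 lists as its first aim "Decreased opioid requirements", without naming a route. It then gives IV opioid use as the secondary endpoint, widens this to oral doses ("The IV and PO opioid doses will be quantified at 1, 24, 48, 72, and 96 hours") and defines the analysed variable: "All the opioid consumption (both PO and IV) will be converted to PO morphine equivalent for analysis".

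Section 4.0 describes the thoracic epidural arm: "epidural bupivacaine 0.05%/hydromorphone 0.05mg/ml mix will be given throughout the duration of their epidural analgesia". The mixes for the rectus sheath arm and the two infiltration arms contain local anaesthetic and saline, and no opioid.

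The study procedures and section 7.0 speak of opioid or narcotic usage with no route. Section 7.0 analyses it over time by repeated measures ANOVA. No section says that epidural hydromorphone is counted, how it would be converted, or that it is left out.

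On timing, the study procedures say "Opioid usage at 1, 24, 48, 72, and 96 hours after the block will be recorded by a member of the research team" and, in the next paragraph, "All these parameters will be measured at 1, 24, 48, 72, and 96 hours after the cystectomy". The same section states that "Thoracic epidural placement will occur in the preoperative period" and that "Both the rectus sheath block and the surgeon infiltration will occur at the end of the case".

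**The concern.** The Background (section 1.0) motivates the aim by the harms of opioid use in general, such as ileus, nausea and longer stay. That rationale is not confined to IV and oral doses. Section 3.0 lists hydromorphone among the study medications, so under section 2.0 hydromorphone given IV or orally is counted in any arm, while the same drug given through the epidural catheter is not.

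The omission follows treatment assignment: it can occur in the epidural arm and in no other. Neither randomization nor a larger sample removes it. A lower IV plus oral total in the epidural arm could then be reported as meeting the first aim, although those patients were receiving opioid by a route that the outcome does not see.

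The recording clock is a separate matter. If opioid use is timed from the block, the windows in the epidural arm start before surgery and those in the other arms start at its end.

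**Working it through.** The plan states no figure for opioid consumption to reproduce. Its only size calculation concerns VAS (section 7.0: coefficient of variation 0.70, ratio of means 1.5, 40 per group, 80% power, two-sided 5%). On the log scale, SD = sqrt(ln(1 + 0.70²)) = 0.631 and the difference is ln 1.5 = 0.405. This gives 39 per group, and power of 0.81 to 0.82 at 40, so the figure reproduces. It does not depend on the opioid outcome.

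**Inputs**
- Hydromorphone concentration in the epidural mix: 0.05 mg/mL (section 4.0).
- Opioid in the assigned mixes of the other three arms: 0 (section 4.0).
- Arms: 4, with 40 subjects each, 160 in total (section 4.0).
- Infusion rate r (mL/h), hours running h, and factor f to oral morphine equivalents: not in the documents.

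**1. Amount not counted.** Per interval, omitted mg = 0.05 × r × h. For r = 1 and h = 24: 0.05 × 1 × 24 = 1.2 mg. As an assumption for scale only, and not a recommendation, rates of 2 to 12 mL/h over a full 24 h would give 0.05 × 2 × 24 = 2.4 mg to 0.05 × 12 × 24 = 14.4 mg.

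**2. Effect on a comparison.** Let D be the mean in the epidural arm minus the mean in another arm, untransformed. Then D(total) = D(IV + oral) + 0.05 × r × h × f − 0. The added term is above 0 whenever the infusion ran in the interval, and it is 0 for an interval after the infusion stopped. Section 7.0 allows a log transformation; the shift is then no longer a constant amount, but its direction is the same.

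**3. Which comparisons.** Four arms give 4 × 3 / 2 = 6 pairs. Three involve epidural and can shift; the other three cannot. The omission concerns 40 of 160 subjects (25%) and is 0 in the remaining 120.

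**4. What cannot be computed.** Without r, h and f there is no morphine-equivalent value for the shift. Only its direction is fixed.

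**5. The clock (separate check).** Let L be the length of surgery, which is not in the documents. For the rectus sheath and infiltration arms, block and end of surgery nearly coincide, so the two stated clocks agree closely. For the epidural arm, the block precedes the end of surgery by at least L. A window of 24 h from the block therefore covers at most 24 − L hours after surgery, and it includes the operation itself. The documents do not say whether intraoperative opioid is counted, so the direction of this effect is not fixed.

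**The case against.** The strongest reply is that the outcome is already defined by route. Section 2.0 names IV, then IV and oral, then both again, and never epidural; the route-free wording elsewhere refers back to that definition. Epidural hydromorphone is part of the assigned method, and what a patient needs beyond the assigned method is a coherent meaning of requirement. On this view one clarifying sentence is enough, and a total-opioid analysis is a matter of preference.

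Much of this stands. IV plus oral opioid is a legitimate measure, and the natural reading of section 2.0 leaves the epidural infusate out. What does not stand is that the plan says so. It never calls the outcome supplemental, places it under a route-free aim, and describes it as all opioid consumption. If the wording is instead taken to include epidural opioid, a recording and conversion rule is missing.

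A reader might also infer more than the documents support:
- *That the plan sets out to claim opioid sparing for epidural.* The hypotheses for epidural in section 7.0 concern VAS, satisfaction, nausea and sedation, not opioid use. The risk lies in how the first aim is interpreted.
- *That every epidural comparison is shifted at every time point.* This holds only for intervals in which the infusion runs, and its duration is not given.
- *That the omission is large in morphine equivalents.* No factor or rate is stated, so no such size can be shown.
- *That opioid harms in the epidural arm are hidden.* Nausea, sedation, ileus and respiratory depression are outcomes in every arm, whichever route the opioid took.
- *That the clock conflict makes the route problem worse.* It is independent of it, and the plan already contains a time zero common to all arms.

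**Conclusion.** The point holds for a secondary outcome and should be corrected before analysis. As defined, the variable supports a statement about supplemental systemic opioid. It does not support a statement about total opioid requirement, because during intervals with a running infusion it leaves out 1.2 mg hydromorphone per 24 h for each 1 mL/h in one arm only. That favours epidural in 3 of 6 pairwise comparisons. The direction rests only on the infusion running and on a positive conversion factor; the size in morphine equivalents is unknown. The VAS primary outcome, its power and the three comparisons without epidural are unaffected.

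The timing conflict in the study procedures is a real but separate inconsistency: one of the two stated clocks gives the epidural arm windows that include surgery.

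**What to change.** For the route:
1. In section 2.0, the study procedures and section 7.0 (outcome list and analysis paragraph), label the outcome *supplemental systemic (IV+PO) opioid, excluding epidural hydromorphone*.
2. Record the epidural volume infused over the same intervals as the other opioid data, and report hydromorphone in mg (mL × 0.05) by time point.
3. Add one sensitivity analysis of total opioid (IV, oral and epidural), using the same repeated measures model and a pre-specified range of conversion factors.
4. State that a lower IV plus oral total alone supports only reduced supplemental opioid.

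For the clock, as a separate edit: reconcile the two statements in the study procedures to one time zero common to all four arms, such as the post-cystectomy time already stated there.

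The cost is wording in four places plus the timing sentence, at most 5 × 40 = 200 volume entries, and one extra analysis. The downside is that this analysis may be inconclusive, because the epidural conversion is uncertain. The label and the report in mg need no conversion factor and hold regardless. No change to treatment is involved.

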### **3.0 Inclusion/Exclusion**

Inclusion criteria:

- Patients undergoing cystectomy surgery
- ASA class 1, 2, 3 or 4
- Age 18 or older, male or female
- Desires Regional anesthesia for postoperative pain control

Exclusion criteria:

- Any contraindication for thoracic epidural, such as coagulopathic states or pre-existing hardware in the thoracic epidural space.
- History of substance abuse in the past 6 months.
- Patients on more than 30mg morphine equivalents of opioids daily.
- Any physical, mental or medical conditions which in the opinion of the investigators, may confound quantifying postoperative pain resulting from surgery.
- Known allergy or other contraindications to the study medications (Acetaminophen, Gabapentin, Bupivacaine, Hydromorphone).
- Postoperative intubation.
- Any patient with history of neuropathic bowel or bladder dysfunction

